6.7. Derived and Transformed Data

6.7.1. Baseline Age

Baseline age is the age at the time of randomization.

6.7.2. Study Day

Study day will be calculated from the first dosing date of study drug (FDD) and derived as follows:

- Assessment date \geq date of first study drug: Assessment Date FDD + 1
- Assessment date < date of first study drug: Assessment Date FDD.

If a subject is randomized but does not receive any study drug, the randomization date will be used for reference, in place of FDD.

Relative symptom start day will be calculated from the symptom start date and derived as follows:

• FDD – symptom start date +1

6.7.3. Change from Baseline

Where applicable, change from baseline will be computed simply as the difference between the post-baseline value and the baseline value.

6.7.4. Visit Windows

For the purposes of by-visit analyses for scheduled clinical assessments (i.e., excluding patientreported assessments), visit windows for inclusion in the analysis are defined in Table 3. Note that the definition of baseline is provided in Section 6.6.

Visit	Target Study Day	Visit Window, Study Day(s)		
Baseline/Day 1 ^a	1	1		
Day 3	3	2-4		
Day 5	5	4-6		
Day 7	7	7 – 10		
Day 14	14	11 – 21		
Day 29	29	22 - 36		
Day 60	60	>36		
a. If a Day 1 assessment is not available, a qualifying baseline assessment can be utilized.				

Table 3:Visit Windows (Days)

Patient reported outcomes are to be reported daily on Days 1-29 and data will be based on the corresponding day. If there is more than one assessment on a day, then the least favorable assessment will be utilized for analysis.

There is overlap at study day 4 for the Day 3 and Day 5 windows to increase the chance to have qualifying observations at both of these timepoints. In the case where a measurement is captured on Day 4, the assignment for the observation will be according to the following:

- If there is another measurement on study day 5 and:
 - Another qualifying measurement for Day 3: day 4 measurement not assigned to Day 3 or Day 5
 - Otherwise, day 4 measurement assigned to day 3 and day 5 measurement assigned to Day 5.
- Else if there is another measurement on study day 6 and:
 - Another qualifying measurement for Day 3: day 4 measurement not assigned to Day 3 or Day 5
 - Otherwise, day 4 measurement assigned to Day 3 and day 6 measurement assigned to Day 5.
- Else day 4 measurement is assigned to Day 5.

6.7.5. Multiple Assessments

If multiple measurements are obtained within a visit window for a subject, the value obtained closest to the target timepoint will be used. For any visit, no more than one value per subject will be included in an analysis. In the event of multiple observations that are equidistant from, but not on, the target day (i.e., observations made in a similar time frame before and after target), the later value, based on date and time, will be selected.

6.8. Handling of Missing Data

6.8.1. Missing Efficacy Endpoints

Missing efficacy data will not be imputed unless otherwise specified in the specific section describing an endpoint. Sensitivity analyses will be carried out to evaluate the impact of missing efficacy data.

6.8.2. Missing Start and Stop Dates for Prior and Concomitant Medication

Where the start date for a concomitant medication is missing, the medication will be assumed to have started prior to enrolment in the study. Where the stop date for a concomitant medication is missing, the medication will be assumed to be ongoing to the date of the subject's last assessment.

6.8.3. Missing Start and Stop Dates for Adverse Events

Where the entire start date for an adverse event is missing, the adverse event will be assumed to be treatment-emergent. In this case, if the duration of an adverse event is computed, the start date will be considered as the date associated with Day 1. If the month and year of an adverse event is provided, then the start date will be considered as the later date between the first day of the month/year and the treatment start date.

Where the stop date for an adverse event is missing, the adverse event will be assumed to be ongoing to the date of the subject's last assessment. If the month and year of the stop date is provided, then the stop date will be considered as the earlier date between the last day of the month/year and the last assessment date.

6.8.4. Missing Numeric Viral Load Assessment

Where SARS-CoV-2 RNA is detected but the numeric value is "<500", it will be assigned as LLoQ-1 (i.e., 499). If SARS-CoV-2 RNA is not detected, it will be imputed as LOD – 1 (i.e., 249). If SARS-CoV-2 RNA is ">50000000", it will be assigned as 500000001 for the purpose of quantitative summaries. For samples reported outside the limits of quantification (e.g.., '<500', or '>500000000'), listings will display "<500" or ">500000000", as appropriate.

6.8.5. Missing COVID-19 symptom diary assessment

If a subject was missing all symptom diary assessments, this subject will be excluded from analysis. For the time-to-event analyses, missing individual symptom assessments at times will be imputed prior to statistical analysis. If there is missing data between two assessments, the missing data will be imputed as the worst outcome of the two. Missing data after the last recorded assessment will not be imputed; instead censoring may be utilized for the time to event endpoint in cases where the endpoint was not achieved. For time to sustained alleviation/improvement of symptoms, censoring will be applied thus:

- if the last observed time point does not meet alleviation/improvement criteria, the result is censored at the time of the last recorded result
- if the last observed time point meets alleviation/improvement criteria but the requirement for sustainment (i.e. criteria not maintained over 4 day period) has not yet been met, the result is censored using the approach described in Section 8.8.

Missing baseline assessments will be imputed according to the following rules: 1) missing individual symptoms and worst severity of COVID-19 symptoms will be imputed as 'mild'. 2) Missing assessments for "loss of taste" and "loss of smell" will be imputed as 'no'. 3) Missing general physical health will be imputed as "fair". 4) Missing returned to usual health will be imputed as "no". 5) Missing symptom relapse will be imputed as "not applicable".

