3.2. Study Endpoints

Estimands corresponding to primary and secondary endpoints are defined in Table 2.

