Secondary: difference in the proportion of subjects in the supportive-care-only population with COVID- 19-related complications by Day 29 and Day 60, regardless of intercurrent events	The proportion of subjects in the supportive-care-only population with COVID-19- related complications through Day 29 and Day 60	Treatment-policy strategy approach will be taken. Patients are followed, assessed and analyzed irrespective of their completion of the planned course of the study treatment and irrespective of rescue and concomitant therapy.	The common risk difference	The outcome measure up to point of study withdrawal will be used
Secondary: difference in the proportion of subjects in the supportive-care-only population with COVID- 19-related medically attended visits or any cause death by Day 29 and Day 60, regardless of intercurrent events	The proportion of subjects in the supportive-care-only population with COVID-19- medically attended visits or who died due to any cause through Day 29	Treatment-policy strategy approach will be taken. Patients are followed, assessed and analyzed irrespective of their completion of the planned course of the study treatment and irrespective of rescue and concomitant therapy.	The common risk difference	The outcome measure up to point of study withdrawal will be used

				Handling of Missing Data
Estimand	Endpoint	Intercurrent event handling	Population- Level Summary for the Variable	Study Withdrawal/ Lost to Follow- Up
Secondary: difference in the proportion of subjects in the supportive-care-only population who died, regardless of intercurrent events through Day 29 and Day 60	The proportion of subjects in the supportive-care-only population who died due to any cause through Day 29 and Day 60	Treatment-policy strategy approach will be taken. Patients are followed, assessed and analyzed irrespective of their completion of the planned course of the study treatment and irrespective of rescue and concomitant therapy. Death: composite strategy, considered as event	The common risk difference	The outcome measure up to point of study withdrawal will be used

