8.8. Analysis of Exploratory Efficacy Endpoints

The following exploratory endpoints will be examined in both supportive care only and combination antiviral arms.

Time to sustained alleviation or improvement of COVID-19 symptoms

Sustained alleviation/improvement of COVID-19 signs/symptoms is defined as the first occurrence of 4 consecutive days when all symptoms recorded as moderate or severe at study entry are recorded as mild or absent and all symptoms scored mild or absent at study entry are scored as absent. The first day of the 4 consecutive-day period corresponds to the day that the event is achieved. The endpoint will be based on targeted symptoms, which are the 13 symptoms with severities ranging from none to severe in Item 3 of the COVID-19 symptom diary. Subjects who do not achieve the endpoint will be censored according to the following rules:

Case	LOD-3	LOD-2	LOD-1	Last Observed Day (LOD)	Censoring time
1	Not Met	Not Met	Not Met	Not Met	LOD+1
2	Not Met	Not Met	Not Met	Met	LOD
3	Not Met	Not Met	Met	Met	LOD-1
4	Not Met	Met	Met	Met	LOD-2

The cumulative distribution function for time from Day 1 to sustained alleviation/improvement of symptoms will be estimated by Kaplan-Meier methodology and plotted by treatment group. The summary display will include the Kaplan-Meier estimates of proportion achieving the endpoint by day. The analysis will also be carried on subgroups of time from onset of symptoms (<=3 days, > 3days).

Sensitivity analysis will be carried using the same methods for 2 selected subsets of symptoms: 1) runny/stuffy nose, sore throat, cough, feeling hot or feverish, and fatigue; 2) runny/stuffy nose, sore throat, shortness of breath, feeling hot or feverish, headache, and chills; 3) all symptoms from Item 3 of the COVID-19 symptoms diary except fatigue.

Additional subgroup analyses on age group (<65 and >=65), and symptom onset days (<=3 days and >3 days) for time to sustained alleviation of all 13 symptoms will be performed.

Time to self-reported return to usual (pre-COVID-19) health

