Self-reported return to usual health is defined as the occurrence of 4 consecutive days when the response to "Have you returned to your usual (pre-COVID) health?" in question 3 of the COVID-19 symptom diary indicates return to usual health. Analysis and data handling will be the same as that described for the endpoint of time to alleviation or improvement of COVID-19 symptoms. The analysis will also be carried on subgroups of time from onset of symptoms (<=3 days, > 3days).

Proportion of subjects requiring post randomization rescue therapy

Post randomization rescue therapies will be identified by blinded medical review. The number and proportion of subjects requiring post randomization rescue therapy will be tabulated.

Duration and severity of COVID-19 symptom relapse

For subjects who meet the criteria of COVID-19 symptom relapse, duration of relapse will be computed by counting the number of days that the relapse question (i.e., question 4 of the COVID-19 symptom diary) is answered "yes". Severity will be based on the average response to question 1 of the COVID-19 symptom diary during the days where relapse is indicated. Subjects with the last record indicating relapse will have duration of relapse right censored. Kaplan-Meier analysis will be used to summarize symptom relapse duration by treatment group. Severity of symptom relapse will be summarized descriptively. The analysis will also be carried on subgroups of time from onset of symptoms (<=3 days, > 3days).

Proportion of subjects with symptom relapse and viral rebound

The proportion of subjects who meet both the symptom relapse and viral rebound criteria will be compared between the BEM and placebo arms using the same method as in the primary analysis. The analysis will also be carried on subgroups of time from onset of symptoms (<=3 days, > 3 days) and baseline viral load groups (<median, >=median).

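### The exploratory symptom time-to-event analyses censor deaths and permanent diary stops at hospitalization like any other missing diary, which lifts the recovery curves slightly, more in the arm with more events

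*SAP*

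**What the plan says.** SAP 6.8.5 sets three rules for the symptom diary that matter here.

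- Gap between two diaries: "If there is missing data between two assessments, the missing data will be imputed as the worst outcome of the two".
- After the last diary: "Missing data after the last recorded assessment will not be imputed; instead censoring may be utilized for the time to event endpoint", where the endpoint was not reached.
- Last diary not meeting the criteria: "if the last observed time point does not meet alleviation/improvement criteria, the result is censored at the time of the last recorded result".

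SAP 8.8, on sustained alleviation or improvement, says: "Subjects who do not achieve the endpoint will be censored according to the following rules". Its table censors at LOD+1, LOD, LOD-1 or LOD-2 (LOD is the last observed day), depending on how many of the final days met the criteria. For self-reported return to usual health, 8.8 says: "Analysis and data handling will be the same as that described for the endpoint of time to alleviation or improvement of COVID-19 symptoms". Both endpoints are summarized by Kaplan-Meier.

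None of this text mentions death or hospitalization, and no other section supplies a rule. SAP 3.2 says: "Estimands corresponding to primary and secondary endpoints are defined in Table 2". The symptom time-to-event endpoints are exploratory, so Table 2 has no row for them. The one death rule in that table, "Death: composite strategy, considered as event", sits in the all-cause mortality row. SAP Table 4 concerns the hospitalization/death endpoint only.

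**The concern.** Kaplan-Meier estimation treats a censored subject as having the same future chance of the event as those who remain under observation. That is false for a subject who has died, and doubtful for one who was hospitalized and never wrote another diary. Under the trial's own hypothesis these subjects are more frequent on placebo, so the censoring is informative and unequal between the arms. Both recovery curves are pushed up, the placebo curve more. Whatever part of a recovery difference arises through death or lasting illness in hospital then largely drops out of the symptom comparison. If the events were more frequent on BEM, the same rule would flatter BEM in these curves.

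**Working it through.** **Inputs from the documents.** Event rates 0.016 (BEM) and 0.04 (placebo), one-sided alpha 0.025, power 90% (SAP 11.2). Evaluable N 2100, allocated 1:1, so 1050 per arm (SAP 4.3.1, 4.4). The documents give no planning figure for the symptom endpoints, so the only figure to reproduce is the sample size that carries these rates.

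**The plan's figure.** With p̄ = 0.028:

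n = [1.960 × √(2 × 0.028 × 0.972) + 1.2816 × √(0.016 × 0.984 + 0.04 × 0.96)]² / 0.024² = 990.9, so 991 per arm and 1982 in total, as stated. 1982 × 1.055 = 2091 (the plan states 2100). 2100 / 0.95 = 2211 (the plan states 2210). Expected serious events: 1050 × 0.04 = 42 on placebo and 1050 × 0.016 = 16.8 on BEM.

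**Assumptions not in the documents.** Everyone else recovers at the same exponential rate in both arms, with a median of 7, 10 or 14 days. A share f = 25%, 50% or 100% of the subjects with a serious event stop the diary for good, on Day 2 to 11, and none of them recovers by Day 29.

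**Day 29 difference if these subjects count as not recovered.** Let F = 1 − 2^(−29/median). Then F = 0.943, 0.866 and 0.762 for medians of 7, 10 and 14 days. An arm with event rate e has (1 − e × f) × F recovered, so BEM minus placebo is (0.04 − 0.016) × f × F.

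| f | median 7 | median 10 | median 14 |
|---|---|---|---|
| 25% | 0.57 | 0.52 | 0.46 |
| 50% | 1.13 | 1.04 | 0.91 |
| 100% | 2.26 | 2.08 | 1.83 |

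(percentage points)

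**Simulation.** With 400,000 subjects per arm, daily Kaplan-Meier, and the log-rank statistic rescaled to 1050 per arm:

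| Quantity | SAP rule (censored when the diary stops) | Counted as not recovered to Day 29 |
|---|---|---|
| Day 29 difference, f = 25% | about 0 | 0.5 to 0.6 points |
| Day 29 difference, f = 50% | about 0 | 0.8 to 1.2 points |
| Day 29 difference, f = 100% | about 0 | 1.7 to 2.4 points |
| Rate ratio, all f | 1.00 to 1.02 | 1.01 to 1.08 |
| Expected log-rank z, all f | 0.0 to 0.4 | 0.3 to 1.6 |

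Across all nine scenarios, the Day 29 difference under the SAP rule lies between −0.1 and +0.3 points. The simulated values in the right-hand column agree with the closed form within simulation error. The median day is the same in both arms and under both rules in every scenario (8, 11 and 15 on the daily grid). The hidden difference cannot exceed 4% − 1.6% = 2.4 points at these rates, and it scales with the difference in event rates.

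**When non-recovery is not certain.** Suppose 80% of the others recover, all serious-event subjects stop the diary on Days 3 to 8, and a share r of them in fact recovers by Day 29. The true difference is 2.4 × (0.8 − r) points. In a simulation of this setting the SAP rule gives 79.7% and 79.9%, a difference of 0.2. Counting everyone as not recovered gives 0.96 × 80 = 76.8% and 0.984 × 80 = 78.7%, a difference of 1.9. The two rules are equally far from the truth when 2.4 × (0.8 − r) = (0.2 + 1.9)/2 = 1.05, so r = 0.8 − 1.05/2.4 = 0.36. At r = 0.5 the truth is 0.7: the SAP rule is off by 0.5 and the alternative by 1.2.

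**The two censoring times.** For a last diary that does not meet the criteria, 6.8.5 censors at the last recorded result, while case 1 of the 8.8 table gives LOD+1. The two sections differ by one day for the same subject.

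**The case against.** A reader might infer that the plan hides benefit or harm. The documents do not support that. Hospitalization and death form the primary endpoint, recur in several secondary endpoints (SAP 3.2.2), and have their own supplemental time-to-event analysis (SAP Table 4). Only the symptom curves lose the effect. Those endpoints are exploratory and outside the testing sequence in SAP 8.5. SAP 8.8 names no test for them and Protocol 8.3.3 calls for descriptive summaries, although Protocol 8.3 mentions the log-rank test for time-to-event endpoints in general. Under the trial's hypothesis the bias also works against BEM, so it would not create a false claim of benefit.

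A reader might also take the top of the range as the expected size. That needs every hospitalized subject to stop the diary permanently and early, and none to recover. The documents do not say that the diary stops in hospital. Protocol 6.7.1 allows the subject's own device, a provided device or paper, with help in recording. Protocol 5.6 lets study drug continue during a hospital stay and encourages subjects who stop it to keep the same assessments. The primary event covers any-cause acute care of more than 24 hours (SAP 8.6.1), so some events may follow recovery or end in it. A subject who resumes the diary is not censored, because the gap takes the worse of the two neighbouring values. The sponsor's prior outpatient Phase 3 study had no deaths (Protocol 1.2.1).

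All of this limits the weight of the point. It also shows that counting every hospitalized subject without a later diary as unrecovered could be less accurate than the present rule. It does not rescue the rule for deaths, where non-recovery is certain, or for permanent diary stops, which the gap rule cannot reach.

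**Conclusion.** The point holds, as a small one. SAP 6.8.5 and 8.8 censor subjects who die, or who are hospitalized and write no later diary, as if their recovery prospects matched those still at risk. Under the assumptions set out above, the rule removes most of a Day 29 difference of about 0.5 to 2.4 points, and the median is unchanged. The recovery pattern and the share who stop the diary are assumptions; only the 4% and 1.6% come from the documents. The effect is confined to exploratory symptom curves and leaves the primary endpoint untouched. For deaths the correction is clear. For hospitalization with no later diary, non-recovery is itself assumed, so a sensitivity analysis is the right place for it. The disagreement between 6.8.5 and 8.8 on the censoring time is a plain inconsistency and needs no assumption.

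**What to change.** In SAP 6.8.5 and 8.8:

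1. State that a subject who dies before meeting the endpoint stays in the risk set as not alleviated (and not returned to usual health) and is censored at Day 29.
2. Add a sensitivity analysis that applies the same rule to subjects hospitalized with no later diary before meeting the endpoint.
3. Keep the present censoring for other missing diaries, and give one censoring time for a last diary that does not meet the criteria.

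The cost is a few sentences, one derivation flag and one extra sensitivity run. Deaths and hospitalizations are already derived for the primary endpoint. SAP section 2 allows revision before unblinding; after that, the change would be reported as a deviation in the clinical study report.

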7. STUDY POPULATION

7.1. Subjects Disposition

The following will be tabulated (number and percentage) by treatment group for the ITT population:

- Received study drug as randomized
- Did not receive study drug as randomized, overall and by reason (e.g., not treated, incorrect treatment received)
- Completed treatment
- Discontinued treatment, overall and by reason
- Completed assessment through Day 29
- Did not complete assessment through Day 29, overall and by reason
- Completed extended follow-up (i.e., to Day 60).
- Did not complete extended follow-up, overall and by reason.

The following will also be tabulated (number and percentage) by treatment for the ITT population:

- Subjects randomized and treated in each country and investigator site
- Subjects randomized and treated by each randomization stratum
- Subjects included and excluded (with reason) for each analysis population.

7.2. Screen Failures

The numbers and proportions of subjects who enrolled but were not randomized will be presented as:

- Screen failures who were not randomized
- Subjects who do not have indication of failing to meet I/E criteria but were not randomized.

Screen failure reasons will also be tabulated. A subject may have more than one reason for screen failure and all reasons for a subject will be counted, i.e., the sum of subjects across screen failure reasons may exceed the total number of screen failures.

7.3. **Protocol Deviations**

A final identification and classification of important protocol deviations will be made prior to the final unblinding of the database and will be documented, in accordance with the study's Protocol Deviations Management Plan. The number and percentage of subjects with important protocol deviations and the total number of important protocol deviations by deviation reason (e.g., nonadherence to study drug, violation of select inclusion/exclusion criteria, lab assessment, randomization, or study procedures, etc.) will be summarized by treatment for the ITT

population. A by-subject listing will be provided for those participants with important protocol deviations.

7.4. Demographic and Baseline Characteristics

To review treatment group comparability within the study, a number of variables collected at baseline will be presented by treatment groups on the mITT-S, mITT-C and safety analysis populations. No statistical comparisons will be made on these characteristics.

Demographic variables to be summarized include:

- Age
- Age group $(18-49, 50-64, 65 79, \ge 80)$
- Sex
- Race
- Ethnicity
- Country
- Region
- Weight
- Body mass index (BMI).

Baseline Disease Characteristics to be summarized include:

- SARS-CoV-2 RT-PCR viral load at baseline
- SARS-CoV-2 IgG seropositive status at baseline
- Presence of individual high-risk factors (age groups, obesity by age groups, diabetes by age groups, cardiovascular disease by age groups, chronic lung disease by age groups, immunocompromised or immunosuppressed by age groups, other high-risk conditions by age groups)
- Time from symptom onset to study treatment in days
- COVID-19 vaccination status
- Baseline lineage

